#### 10. INTERIM ANALYSIS

No interim analysis is planned.

### 11. DATA CONVENTIONS FOR ANALYSIS

### 11.1 General Statistical Principles

All statistical tests will be performed at the 0.05 (two-sided) level of significance.

All observed and derived variables (e.g., change from baseline, percentage change from baseline, and response status) that are analyzed or summarized will be listed by subject. Descriptive statistics will provide an overview of the efficacy and safety results. For categorical parameters, the number and percentage of subjects in each category will be presented. The denominator for percentage will be appropriate for the purpose of the analysis. For continuous parameters, descriptive statistics will include number of subjects, mean, standard deviation (SD), median, minimum, and maximum.

### 11.2 Study Day

Day 1 is the date of first study drug administration. As subjects apply study drug under supervision on the day of randomization, this will generally be the day of the Baseline Visit. Study day is calculated relative to the date of Baseline (Day 1).

### 11.3 Baseline and Change from Baseline

Baseline value is defined as the last non-missing value prior to the first dose of study drug. Change from baseline is defined as the post-baseline value minus the baseline value unless otherwise specified. Percent change from baseline is calculated as follows: Percent change = (Change from baseline / Baseline) \* 100.

### 11.4 Analysis Visit Window

All efficacy and safety endpoints will be analyzed according to the nominal visits (i.e. actual visit) except for assessments collected on early termination and unscheduled visits. Early termination and unscheduled visits will be re-numbered to an analysis visit based on their windowed visits defined by actual study day. If more than one visit occurs within a single visit window, then the analysis will take the one closest to the target day. If the 2 visits are equidistant from the target day, the visit with later date and time will be used.

The following analysis visit windows will apply to early termination and unscheduled visits:

Visit	Week	Target Day	Analysis Window
2	Baseline	1	On or prior to Day 1
3	2	15	Post first dose – Day 21
4	4	29	Day 22 – Day 42
5	8	57	Day 43 – Day 70
6	12	85	Day 71 – Maximum (last day of treatment + 3 days,
			Day 87)
7	16	113	> Maximum (last day of treatment + 3 days, Day 87)

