#### 6.3.4. Clinical Safety Laboratory Assessments

All protocol-required laboratory assessments must be conducted in accordance with the Study Reference Manual or Laboratory Manual and the protocol Schedule of Assessments (Table 1). Laboratory requisition forms must be completed, and samples must be clearly labeled with the subject number, protocol number, site/center number, and visit date. Details for the preparation and shipment of samples will be provided by the laboratory and are detailed in the Study Reference Manual or the Laboratory Manual. Reference ranges for all safety parameters will be provided to the site by the laboratory responsible for the assessments.

A list of clinical laboratory tests and parameters is provided in Table 3.

All laboratory tests with values that are considered clinically significantly abnormal during participation in the study should be repeated until the values return to normal or baseline. If such values do not return to normal within a period judged reasonable by the Investigator, the etiology should be identified, if possible, and the Sponsor notified.

Clinical Study Flotocol - Ve

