#### 8.1.3. Adverse Events of Special Interest

In prior clinical studies, the following AEs have been identified as AEs of particular clinical importance and will be reported as AESIs in this study; in each case study drug may be discontinued, based on Investigator judgment, and may be restarted when the event resolves:

- Contact dermatitis: the study site should collect location, duration, size, associated symptoms (itching, burning, pain), severity (mild, moderate, severe), and photograph the affected site (if possible). If the subject contacts the study site to report significant skin irritation at or near the site of study drug application between study visits, the subject should be brought in for an unscheduled visit, if possible.
- Folliculitis: the study site should collect the location, duration, size, associated symptoms (itching, burning, pain), severity (mild, moderate, severe), indicate whether pustular, and photograph the affected site (if possible).
- Headache: the study site should collect duration, severity (mild, moderate, severe), onset, and location (e.g., frontal, temporal, occipital, diffuse).

Additional AESIs may be identified by the Drug Safety Physician and if applicable by the Clinical Study Team Physician during the evaluation of safety data for the Clinical Study Report. For each AESI, a narrative may be written and included in the Clinical Study Report.

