### 12.9.3 Clinical Laboratory Testing

All clinical laboratory (hematology, clinical chemistry, urinalysis) values will be listed by subject. The reference normal ranges and reference range indicators (e.g. high, low, normal etc.) will be supplied by the central laboratory and displayed in the data listings. For the purpose of shift table summaries, the central lab reported reference range indicators will be classified as low, normal and high accordingly based on the table below. Change from baseline in abnormality status will be summarized using shift tables. For urinalysis, only lab tests with numeric results reported are included in shift tables. Separate listings will identify subjects with markedly abnormal values. For quantitative measures, observed values and changes in clinical laboratory values will be summarized descriptively by visit and treatment group.

Reference Range Indicator in Shift Tables	Reference Range Indicator Reported by Central Lab	
Low	Low, Low Level 1 Alert, Low Lever 2 Alert	
Normal	Normal	
High	High, High Level 1 Alert, High Level 2 Alert	

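### SAP 11.4's one-visit-per-window rule covers safety data and no worst post-baseline shift is planned, so abnormal unscheduled or early-termination labs can be left out of the by-arm lab tables

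*SAP*

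**What the plan says.** SAP 11.4 opens with its scope: "All efficacy and safety endpoints will be analyzed according to the nominal visits", with an exception for assessments made at ET and unscheduled visits. For those, "Early termination and unscheduled visits will be re-numbered to an analysis visit based on their windowed visits defined by actual study day". It then gives the selection rule, "If more than one visit occurs within a single visit window, then the analysis will take the one closest to the target day", and the tie rule, "If the 2 visits are equidistant from the target day, the visit with later date and time will be used". The windows are:

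- Week 2: "Post first dose – Day 21", target Day 15
- Week 4: Days 22 to 42, target Day 29
- Week 8: Days 43 to 70, target Day 57
- Week 12: Day 71 to the later of Day 87 and last treatment day + 3, target Day 85

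On laboratory data, SAP 12.9.3 says "Change from baseline in abnormality status will be summarized using shift tables" and adds descriptive summaries by visit and treatment group. It does not say whether the shift tables are by visit. It gives no worst-value rule and no exemption from 11.4. It does list every value, with a separate listing of markedly abnormal ones.

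The protocol generates extra safety records. Section 6.3.4 says that tests with values "considered clinically significantly abnormal during participation in the study should be repeated until the values return to normal or baseline". Under Section 8.1.3, when significant irritation is reported between visits, "the subject should be brought in for an unscheduled visit, if possible". Section 7.5 and Table 1 require blood labs at the ET visit.

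**The concern.** Unscheduled and ET safety records are often made because something has gone wrong. A rule that picks the record nearest a calendar target takes no account of that. It can leave out the on-treatment lab closest to an early withdrawal, or an abnormal value found between visits. Read literally, it can also put a normalised repeat in place of the abnormal value that prompted it.

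Blood labs are scheduled on treatment only at Weeks 4 and 12, so each omitted value matters. Clinically significant laboratory change from baseline is a stated safety endpoint. Protocol 1.3.1.2 reports liver findings and secondary haematological findings in animals, and Section 8.6 provides no independent data monitoring committee. The shift tables are the by-arm laboratory summary that does not depend on an investigator judging a value clinically significant.

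**Working it through.** The plan states no figure on this point to reproduce. The check applies the rule of SAP 11.4 day by day.

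**Inputs.** Windows, targets, selection and tie rules: SAP 11.4. Visit tolerance ±2 days at Weeks 2 to 12, and blood labs at Screening, Weeks 4, 12 and 16 and ET: Protocol Table 1.

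**Rule.** Let t be the target day, d the scheduled day and r the day of another record in the same window. Record r is used if |r − t| < |d − t|, or if the two are equal and r is later. Otherwise d is used.

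**1. ET lab after Week 4.** With d = t = 29, |d − t| = 0. For r = 30 to 42, |r − t| = 1 to 13, so the ET lab is always dropped. An ET lab on Day 36, for example, has distance 7 against 0. For ET on Days 32 to 42 the distance is 3 to 13. A Week 4 visit within tolerance is at most 2 days from target, so the ET lab is dropped whichever in-tolerance day the Week 4 lab was taken.

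**2. A repeat after an abnormal scheduled lab (literal reading).** If the visit was e days early (d = t − e) and the repeat comes L days later, then |r − t| = |L − e|. This is at most e when L ≤ 2e. Displacement therefore needs an early visit and a repeat within twice the number of days it was early.

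| Week 4 lab on | Displaced by a later repeat on |
|---|---|
| Day 27 | Days 28–31 |
| Day 28 | Days 29–30 |
| Days 29, 30, 31 | never |

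Week 12 has the same pattern: Day 83 is displaced by Days 84–87, Day 84 by Days 85–86, and Days 85–87 never.

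To give a share, assume scheduled Days 27 to 31 equally likely and repeat lags equally likely:

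- Lags 1–3: Day 27 contributes 3 cases and Day 28 contributes 2, so 5/15 = 33%.
- Lags 1–7: Day 27 contributes 4 and Day 28 contributes 2, so 6/35 = 17%.

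Both are conditional on an abnormal lab that is repeated. The documents give no repeat timing.

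**3. Abnormal values between visits.** Take labs on Days 29 and 85 and the Week 12 window closing on Day 87. Days 2 to 87 are 86 days, less the 2 lab days = 84.

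- If the rule selects laboratory records: dropped on Days 22–42 except 29 (20 days) and Days 71–87 except 85 (16 days), so 36 of 84. Kept on Days 2–21 (20 days) and 43–70 (28 days), so 48 of 84, because no lab is scheduled in those two windows.
- If the rule selects whole visits, all on target: clinic visits on Days 15, 29, 57 and 85 leave 86 − 4 = 82 other days, and an unscheduled visit on any of them is dropped.

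Vital signs are taken at all four of these visits, so the second result applies to them on either reading.

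**4. The reverse case.** A Week 4 lab on Day 31 loses to an unscheduled lab on Days 28 to 30. If the scheduled value was normal and the unscheduled one abnormal, the rule adds a shift.

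**The case against.** **The tie-break may not reach scheduled visits.** SAP 11.4 analyses scheduled assessments by nominal visit and says the windows apply to ET and unscheduled visits. The closest-to-target rule could then be meant only to choose among re-numbered visits. This is a fair reading, and it removes the displacement in step 2. It does not close the gap: if the scheduled record always stands, unscheduled and ET values are left out whenever one exists.

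**By-arm evidence exists elsewhere.** This stands in large part:

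- Under Protocol 8.1.1, abnormal labs judged clinically significant are adverse events, and SAP 12.9.1 tabulates treatment-emergent events by arm and maximum grade.
- The irritation visit belongs to contact dermatitis, an event of special interest, for which SAP 12.9.1 summarises the most extreme level of each characteristic.
- SAP 12.9.4 tabulates markedly abnormal vital-sign changes, without saying which records feed the table.

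What remains is that the adverse-event route depends on investigator judgement, 12.9.3 defines no threshold for markedly abnormal labs, and a listing is not a by-arm summary.

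**The protocol does not ask for a worst-value shift.** Correct. Section 10.4.3 asks for by-visit summaries, and shift tables if applicable. The case for the addition is that it is good practice and cheap, not that the SAP breaches the protocol.

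**Inferences to resist.** A reader might conclude that between-visit values never reach the shift tables. Steps 3 and 4 show that some do. A reader might also infer a systematic bias towards no shift, but the rule uses dates and ignores values, and step 4 works the other way. Finally, a literal reading would let an unscheduled Day 85 PGA replace a Week 12 PGA taken on another day. However, the schedule plans no unscheduled PGA and any effect has no stated direction, so this is not a finding against the primary endpoint.

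**Conclusion.** The point holds in limited form. SAP 11.4 applies single-record selection to safety data, and SAP 12.9.3 has no worst post-baseline shift. Abnormal unscheduled or ET labs can therefore be absent from the by-arm by-visit and shift tables. The ET case does not depend on displacement of a scheduled value: a Day 29 lab excludes an ET lab on any of Days 30 to 42, whether the rule is read as selecting visits or records. It assumes only that the shift tables follow the 11.4 analysis visits, which 12.9.3 leaves unstated. Replacement of an abnormal scheduled lab by its repeat is narrower: it needs the literal reading, an early visit and a quick repeat. The 33% and 17% rest on assumed uniform timing and should not be read as expected rates.

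The values are not lost from reporting. The number of subjects affected is not known, and nothing here bears on the efficacy conclusion. The change is worth making before unblinding, because as written the rule can leave out the values a safety shift table is meant to show.

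**What to change.** 1. **SAP 11.4.** State that for laboratory and vital-sign data, and for LTS by-visit summaries, the scheduled-visit value is used whenever it exists, and that unscheduled or ET values only fill a missing one. This settles the displacement question. On its own it would leave more unscheduled values out, so it needs item 2.
2. **SAP 12.9.3 and 12.9.4.** Add by-arm shift tables from baseline to the worst post-baseline value, lowest and highest, using all scheduled, unscheduled and ET records. For blood labs and vital signs, count values up to last dose + 3 days. For urinalysis, count values through the final visit, because Table 1 schedules it after baseline only at Week 16 and ET. With a last dose on Day 84 (84 + 3 = 87), a lab on any of the 84 days in step 3 could reach the table.
3. **SAP 12.9.2.** LTS is first collected at Week 2 and has no baseline, so summarise the maximum post-baseline score by arm instead of a shift.

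The cost is a few sentences and a few extra tables. No new data are needed.

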### 11.5 Study Centers

There will be approximately 50-60 study sites in the United States (US) and Canada.

The primary and secondary efficacy endpoints will be summarized by study site using descriptive statistics. Exploratory analyses of the primary and secondary endpoints may be performed to elucidate any identified sources of heterogeneity in the results.

### 11.6 Multiple Comparisons

Multiple comparisons of the secondary endpoints will be controlled using the Fixed-Sequence method. Hypotheses testing for the secondary efficacy endpoints will only be conducted if the primary efficacy endpoint has demonstrated statistical significance at 0.05 two-sided in favor of tapinarof. Testing of the secondary endpoints will be performed sequentially following the below pre-specified order (see details in Section 12.7.2):

- Proportion of subjects with  $\geq 75\%$  improvement in PASI from Baseline at Week 12
- Proportion of subjects with a PGA score of 0 or 1 at Week 12
- Mean change in %BSA affected from Baseline to Week 12
- Proportion of subjects with ≥90% improvement in PASI score from Baseline to Week 12

Hypothesis testing for secondary endpoints will stop if statistical significance at 0.05 two-sided in favor of tapinarof is not observed.

### 12. STATISTICAL EVALUATION

### 12.1 Subject Disposition

The number and percentage of subjects screened, screen failed along with reason for screen failures, randomized, included in each analysis population, completing 12-Week Double-Blind treatment, completing the study, withdrawing from treatment (together with the reasons for withdrawal), withdrawing from the study (together with the reasons for withdrawal), and subjects

excluded from PP population (together with the reasons for exclusion) will be summarized using frequencies and percentages by treatment group. For subjects who have completed the 12-Week treatment, the number and percentage of those who elect to enroll in the open-label study will be summarized.

Enrollment and disposition will be listed by subject. Screen failures and subjects not randomized will also be listed by subject.

The number of days in the study (date of study completion / discontinuation minus date of Day 1 plus 1) will be summarized descriptively by treatment group.

### 12.2 Protocol Deviations

Protocol deviations will be listed by subject. Protocol deviation categories (major vs minor) will be summarized by treatment group.

### 12.3 Demographic and Baseline Characteristics

Demographics and baseline characteristics will be summarized overall and by treatment for the ITT, PP and Safety populations. The following demographic and baseline variables will be included:

- Age
- Gender
- Race
- Ethnicity
- Weight
- Height
- BMI
- Baseline PGA
- Baseline PASI score
- Baseline %BSA Affected

### 12.4 Study Medication Exposure and Compliance

The following exposure and compliance parameters will be summarized descriptively by treatment group:

• Total number of days exposed, defined as date of last dose of study drug minus date of first dose of study drug plus 1.

- Number of doses administered, calculated from the subject dose diary. If a subject does not return diary or returns the diary with missing dosing record, the number of doses taken during that period is assumed to be 0.
- Grams (g) of study drug administered, total and average per day. Drug administered is calculated as the summation of the difference between dispensed weight and returned weight for all returned tubes. Unreturned tubes will be assumed unused and will be included as 0 gram in amount drug used calculation.
- Percent compliance will be calculated as the number of doses administered over the number of days exposed.
- Subject compliance, defined as ≥80% compliance over the entire duration of study. If the percentage of study medication compliance is unknown, the subject is assumed to be non-compliant with study medication.

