### **Investigational Product, Dosage and Mode of Administration:**

Tapinarof cream, 1% is a white to off-white cream containing 1% (10 mg/gram) tapinarof, supplied in 30-gram tubes, and is to be self-administered once daily via topical application of a thin layer to affected areas.

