## 5.4. Compliance with Study Drug Administration

At baseline, study staff will provide the subject with detailed instructions concerning protocol requirements and use of study drug. Additionally, subjects will be asked to complete a daily diary with the time of each application of study drug. At each post baseline study visit, study staff will review use of study drug, as applicable, with the subject.

When subjects are dosed at the site, they will apply the study drug under supervision of the study staff. The date and time of each dose administered in the clinic will be recorded in the source documents. The study drug and study subject identification will be confirmed at the time of dosing by a member of the study site staff other than the person dispensing the study drug.

At the time of dispensing study drug to each subject, site personnel will weigh the tubes to be dispensed and will record the weight of all tubes dispensed at each visit in the drug accountability logs. Subjects will be instructed to bring all used and unused tubes with them to each study visit. Site personnel will weigh the returned tubes (used and unused) and record the weight in the drug accountability logs. If a tube has been lost, discarded, or forgotten by the subject, then the site personnel will make a notation of this on the drug accountability logs. The site personnel will remind the subject to keep all tubes of study drug dispensed and to bring all used and unused tubes to each clinic visit. These data will be used to estimate subject compliance with use of study drug. Tubes of study medication dispensed at the most recent prior visit which remain unopened (the foil cap on the tube remains fully intact/undisturbed) may be re-dispensed to study subjects at the current visit. Opened, partially used tubes or tubes with foil overlay removed are not to be re-dispensed to study subjects. If there is any question as to re-dispensation, sites should issue new tubes of study medication to the subject(s).

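### Counting every unreturned tube as 0 g used can only push the summaries of total grams and grams per day downward, by an amount the documents do not allow anyone to fix

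*SAP*

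**What the plan says.** SAP section 12.4 lists among its descriptive exposure parameters "Grams (g) of study drug administered, total and average per day". The calculation is: "Drug administered is calculated as the summation of the difference between dispensed weight and returned weight for all returned tubes". Tubes that do not come back are then given a value: "Unreturned tubes will be assumed unused and will be included as 0 gram in amount drug used calculation".

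The same section defines exposure time separately, as "Total number of days exposed, defined as date of last dose of study drug minus date of first dose of study drug plus 1". It does not say which number of days divides the grams in the daily average.

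Protocol section 5.4 has sites weigh tubes at dispensing and at return and asks subjects to bring every tube to each visit. It also foresees gaps: "If a tube has been lost, discarded, or forgotten by the subject, then the site personnel will make a notation of this". The SAP makes no use of that notation and plans no alternative summary of grams.

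**The concern.** The rule replaces an unknown amount by its smallest possible value. Protocol section 5.4 names three reasons why a tube may be missing: lost, discarded or forgotten. None of them implies that the tube was never opened, and a discarded one may well be empty. Every error made by the rule therefore runs in the same direction, and more data will not average it out.

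The quantity matters because the dose is a thin layer on affected skin, in subjects whose affected area may be anywhere from 3% to 20% of body surface. Days exposed and number of doses say how often cream was applied; only grams say how much. What is at stake is whether the study report describes that quantity correctly.

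Non-return need not be rare. Protocol section 10.2 and SAP section 7 allow for up to 25% of subjects lost to follow-up by Week 12, and a subject who never comes back cannot hand in the last tubes dispensed. That figure is a planning allowance for subjects, not a tube return rate, so it gives a reason to count unreturned tubes but no estimate of their number.

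**Working it through.** The plan states no figure for grams used, for tubes returned or for this bias, so there is nothing of its own to reproduce.

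**Inputs from the documents**
- Use credited to an unreturned tube: 0 g (SAP 12.4).
- Use credited to a returned tube: weight dispensed minus weight returned (SAP 12.4).
- Most that a tube can contribute: 30 g. The cream is "supplied in 30-gram tubes, and is to be self-administered once daily" (Protocol synopsis, investigational product).
- Exposure days: first to last dose, which does not depend on whether tubes come back (SAP 12.4).

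**Inputs that must be assumed**
- f, the share of dispensed tubes not returned.
- k, mean use per unreturned tube divided by mean use per returned tube.

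**Formula.** Per dispensed tube, in units of the mean use of a returned tube, the true amount is (1 − f) + f·k and the SAP reports (1 − f). The relative shortfall is

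f·k / (1 − f + f·k).

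It is never negative. With f above zero it is zero only when k = 0, and it equals f only when k = 1. If grams per day divides by days exposed, the daily average has the same shortfall, because the divisor does not change.

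**Results over assumed f and k**

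| f | k = 0 | k = 0.5 | k = 1 | k = 1.5 | k = 2 |
|---|---|---|---|---|---|
| 2% | 0% | 1.0% | 2.0% | 3.0% | 3.9% |
| 5% | 0% | 2.6% | 5.0% | 7.3% | 9.5% |
| 10% | 0% | 5.3% | 10.0% | 14.3% | 18.2% |
| 20% | 0% | 11.1% | 20.0% | 27.3% | 33.3% |

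The k = 2 column is the case where unreturned tubes were emptied (30 g) and returned tubes averaged 15 g: 30/15 = 2. At f = 10% this gives 0.10 × 2 / (0.90 + 0.20) = 18.2%.

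**One subject, all usage figures assumed.** Ten tubes are dispensed over 84 days (12 weeks), nine come back with 20 g used from each, and one does not come back. The SAP reports 9 × 20 = 180 g, or 180/84 = 2.14 g/day.

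| Missing tube | True total | True g/day | Shortfall |
|---|---|---|---|
| Unused (0 g) | 180 g | 2.14 | 0% |
| Used like the others (20 g) | 200 g | 2.38 | 10.0% |
| Emptied (30 g) | 210 g | 2.50 | 14.3% |

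**Where grams go next.** Protocol section 5.4 says of the tube weights: "These data will be used to estimate subject compliance with use of study drug". The SAP does otherwise: "Percent compliance will be calculated as the number of doses administered over the number of days exposed", with doses counted from the diary. The 80% compliance criterion for the per-protocol population (SAP section 8) refers to that diary-based figure. SAP section 12.10 scales plasma concentration by baseline affected body surface area, and the adverse event summaries in section 12.9.1 are by treatment. None of these takes grams as an input.

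**The case against.** The rule is prespecified, open and applied in the same way to both arms of a blinded study, and it feeds only a descriptive table. Protocol section 5.4 works to keep non-return low through instructions and reminders. It also provides for tubes still unopened at the next visit, so an unused tube that never comes back is plausible. A lost or forgotten tube says nothing about how full it was. All of this stands. It limits the size and reach of the error but does not change its direction.

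Four stronger readings are tempting, and the documents do not support them:

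- **The bias equals the share of tubes not returned.** That needs k = 1, which neither document states. It is also hard to combine with the argument that discarded tubes tend to be empty, which points to k above 1.
- **The SAP keeps the affected days in the divisor.** Days exposed is the likely divisor, but the SAP does not name one.
- **The error carries into compliance, the per-protocol population, safety or PK results.** The protocol's stated purpose for the weights invites this, but no planned SAP analysis on those topics uses grams.
- **The comparison of grams between arms is distorted.** That would need non-return, or use of unreturned tubes, to differ by arm. The documents give no evidence either way.

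**Conclusion.** The point holds as a one-sided error in the only planned measure of how much cream was applied. Its direction follows from the SAP's own rule and needs no assumption beyond some unreturned tubes having been used. Its size is unknown: the 0%, 10% and 18% at 10% unreturned are illustrations that rest on an assumed return rate and on assumed use per tube, and equal use is not the worst case. The consequence is confined to the descriptive exposure summary, so this is a minor improvement and no threat to the trial's conclusions.

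**What to change.** In SAP section 12.4, replace the 0 g assumption as follows:

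1. Treat use from an unreturned tube as missing.
2. Report average grams per day over dispensing intervals in which every tube came back, and state that the divisor is the number of days in those intervals.
3. Report the number and share of unreturned tubes by arm.
4. Give total grams as a range, with 0 g per unreturned tube as the lower bound and 30 g as the upper bound. For the subject in the example this is 180 g to 210 g.

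The present result survives as the lower bound, so nothing is lost. Simply dividing reported grams by (1 − f) is not a substitute, because it corrects the total only when k = 1.

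The cost is a wording change and minor programming on weights and notations that sites already record. The downside is that some intervals drop out of the average, and the average then assumes that use in complete intervals resembles use in the others. That assumption cannot be checked from the tube weights, which is why the bounds should stand beside it.
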